the project (https://github.com/[name]/A-large-multi-site-test-of-self-administered-mindfulness).

Participants and sites

Because the guided audio meditations and the active control excerpts recorded for this experiment were in English, we limited the study to English native speakers or participants who self-assessed their level of English proficiency at the C1/C2 levels from the Common European Framework of Reference for Languages (Council of Europe, 2001).

Participants were excluded if they reported having or having had a history of mental illnesses, if they declared having meditated in the previous 6 months, or if they were not fluent in English. Each participant was asked to take part in the survey using a smartphone with headphones or earphones attached, not a computer or laptop, because one experimental condition included mindful walking and, participants being randomly allocated to conditions, we needed to ensure that everyone was equally capable to perform any of the mindfulness activities. Each site was asked to collect data from at least 70 participants and up to a maximum of 130 participants⁵ in order to be considered for authorship of the article resulting from this experiment.

The data collection will start on March 23th 2022. Sites will be able to begin recruiting participants up to three weeks after the actual data collection begins. Sites that fail to start data collection up to three weeks from the start of the effective date will be excluded from the project.

Bayesian design analysis

Prior to the data collection, we simulated data based on a Bayes Factor Design Analysis (BFDA; Schönbrodt & Wagenmakers, 2018) to assess the expected efficiency and informativeness of the present design. More specifically, the aim of the design analysis was

⁵ We allowed a maximum of three people, per site, to become part of the authorship team.

to establish (1) the expected likelihood of the study to provide compelling relative evidence either in favor of H_0 ($BF_{01} = 1/10$) or H_1 ($BF_{10} = 10$); (2) the likelihood of obtaining convincing but misleading evidence, and (3) the likelihood that the study points into the correct direction even if stopped earlier due pragmatic constraints on sample size (Schönbrodt & Wagenmakers, 2018).

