Given these aims, we modeled a sequential design with maximum *N* where the data collection continues until either the threshold for compelling evidence is met or the maximum *N* is reached. Initially, forty-one labs indicated interest in the project, we expect to have up to 30 data-collecting labs. Each lab was expected to collect data of at least N = 70 participants, with a stopping *N* at 120 (translating to *Min* = 420 and *Max* = 720 participants per condition). We intended to be able to detect an effect size of *d* = 0.20; here we modeled the true value to vary between labs by repeatedly (for each simulation) drawing from a normal distribution, $\delta \sim N(0.20, 0.05)$, with a 95% probability that the effect size falls between *d* = 0.10 and 0.30.

The present study aimed at testing the effectiveness of four stand-alone interventions using a between-subjects adaptive group design, where upon hitting a threshold of compelling evidence in one condition, the plan was to allocate the rest of the participants into other conditions where this has not been the case yet. The design analysis, however, assumed a conservative scenario with equal *N* across all conditions, therefore, simplifying the computations to a single between-subjects *t*-test scenario.

The results (see Figure 1) show that, given the assumed design, the probability of the test to arrive at the boundary of compelling evidence (BF = 10 or 1/10) was .79 (.72 at H_1 and .07 erroneously at H_0). The probability of terminating at maximum N of 720 per condition was .21; .05 of showing some evidence for H_1 (BF > 3), .13 of being inconclusive (3 > BF > 1/3), and .03 of showing evidence for H_0 (BF < 1/3). For the test of a single condition against controls, the sequential design is expected to be 27% more effective than collecting a fixed

maximum N per lab, with the average N at stopping point (*BF* boundary and maximum N) at 526. Even conservatively assuming a balanced-N situation, the informativeness of the design thus appears to be adequate and the use of adaptive design is likely to further enhance informativeness and/or resource efficiency. Figure 1 shows the results of the simulation of the sequential design with 10000 iterations.

Figure 1. Design analysis for the sequential bayesian design with maximum N

Procedure

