Participants accessed the experiment via a Qualtrics link. They were provided detailed information about the study (see "Participants Information Sheet" included in the IRB package, https://osf.io/6w2zm/) and were then asked to provide consent prior to participating. Each participant was asked to take part in the survey using a smartphone with headphones or earphones attached, not a computer or laptop, because one experimental condition includes mindful walking and, participants being randomly allocated to conditions, we needed to ensure that everyone would be equally capable to perform the mindfulness activity. To know if this condition was verified we included a question in which we asked participants whether they started the survey from a device other than a smartphone; if they answered negatively,

we asked them to exit the survey and to restart it, this time using a smartphone with headphones or earphones attached.

Participants were also asked to sit in a quiet place such as a room where they could not be disturbed for 20 minutes. After providing informed consent, they were asked to complete the Neuroticism subscale of the IPIP - 5 NEO Domains (IPIP, 2021) to assess the level of neuroticism. Examples of items were "I often feel blue" or "I am filled with doubts about things". Participants could answer a 5-points scale (1 = *Very inaccurate*, 2 = *Moderately Inaccurate*, 3 = *Neither Inaccurate nor Accurate*, 4 = *Moderately Accurate*, 5 = *Very Accurate*). We estimated the scale reliability (i.e., internal consistency) using the omega coefficient. Assuming a unitary-factor model, the reliability estimate in the present sample was $\omega_u = x$.

After the completion of the neuroticism measure, participants were randomly allocated to one of the five conditions⁶. In each condition, participants were presented with a different 15-minutes recording. The four audio files of the mindfulness exercises and the three audio files of the stories of the non-mindful active control condition were recorded by a certified meditator, to keep the voice constant across conditions. Following a brief description of the mindfulness conditions and of the three different stories of the non-mindful active control condition.

Body scan. In body scan, participants were invited to "scan" their parts of the body. Every time the mind wandered, participants were invited to bring back the awareness and the attention to the part of the body they were "scanning".

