To assess whether any of the chosen mindfulness exercises were more effective than the randomly sampled control conditions to reduce stress in participants, we planned to conduct a sequential design. We sampled participants until a Bayes Factor threshold for compelling evidence was met or until a maximally feasible number of participants was collected (Schönbrodt et al., 2017). Unlike in the frequentist approach, the aim of this procedure was not the control of error rates, but to gauge the relative support provided by the present data in favor of one of two competing hypotheses, H_1 and H_0 . In the frequentist approach, the practice of adjusting the sampling plan after peeking at the data would have increased the Type 1 error rate, but in the Bayesian approach, the data collection could be stopped anytime without having any consequences on the interpretation of the Bayes Factor (Rouder, 2014). We divided our analysis workflow into confirmatory and exploratory. The sequential testing was tied to the confirmatory analysis phase while the exploratory analyses had no role in the decisions related to sampling.

Confirmatory analyses

As the aim of the present study was to assess the effectiveness of four stand-alone mindfulness interventions without any aspirations to draw broad inferences about mindfulness intervention in general, we planned to carry out four independent comparisons with the active controls. Therefore, we carried out four independent-samples Bayesian t-tests to determine whether there was a difference between each mindfulness exercise and the active control condition. We employed a two-tailed test using a non-informative JZS Cauchy prior for the alternative hypothesis with a default *r*-scale of $\sqrt{2}/2$ (Rouder, Speckman, Sun, Morey, & Iverson 2009). To account for the hierarchical nature of the data, we compared the condition means using a Bayesian mixed-effects model that involved a random intercept for lab and for different stories used in the non-mindful active control condition.

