⁷ Each time we did so, we generated a file in Rmarkdown that we uploaded on the OSF project page. Similarly, we generated a Rmarkdown file, twice a week, to document how many participants were collected for each site and how many participants were assigned to each experimental group.

⁸ The maximum number of participants was set to 120k, where k is the number of sites that took part in the study, and 120 was the maximum number of participants that each site committed to collect.

⁹70 is the minimum number of participants that we requested to each site to collect to be considered for authorship

Date: 22 March 2022; Swansea University (UK) & Université Grenoble Alpes (France)

thus performed three different Bayesian *t*-tests for each dimension of the Self-Assessment Manikin scale (pleasure, arousal and dominance) comparing our experimental conditions with the control condition. We then looked at The Bayes Factor to establish whether the data favored H_1 or H_0 . Similarly as we did for the confirmatory analyses we compared the condition means using a Bayesian mixed-effects model that involved a random intercept for lab and for different stories used in the non-mindful active control condition to account for the hierarchical nature of the data.

To check whether neuroticism moderated the effects of the four experimental conditions on stress, we compared the model with the interaction to the model with only the main effects (using the lmBF function) and we reported the corresponding BF. If the model with the interaction was preferred to the model with only the main effects of a BF of 10 or more, we would have solid evidence of the moderation of neuroticism on stress. We computed the Markov chain Monte Carlo chain (MCMC) to estimate parameters through the posterior function, in this way for each condition we were able to assess whether there were differences in stress levels for people with high, average, or low neuroticism scores.

Dealing with careless or insufficient effort responder

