We decided to set a series of rules to deal with careless or insufficient effort responders (C/IE; Currant, 2016), to reduce errors and provide more valid results. We decided to be conservative in our criteria by excluding participants that were providing too unrealistic answers that can hardly be due to casual errors, but at most to a consistent pattern in the response modality (i.e., finishing the survey as soon as possible to get payments/credits). Some possible issues were limited by some settings we fixed in the Qualtrics survey; we forced the answers for the questions connected to our exclusion criteria (meditation experience, english level, mental illnesses) for the questionnaires related to our dependent variables/moderator instead the answers were requested¹⁰.

To be sure that participants listened to the 15 minutes mindfulness/control condition we blocked the screen with the audio of the meditation/ control condition for 14 minutes (i.e., 840 seconds) so as not to allow participants to proceed to the following survey page until the meditation was actually finished. However, we excluded participants that completed the survey in less than 946 seconds, because as in addition to the 15 minutes of the recording we added a cut score for response time at 2 seconds an item, by following the recommendations of Huang et al., (2012)¹¹ To exclude participants that provided the same response to every question (i.e., selecting always the answer "strongly agree") we performed a long string analysis. Here we followed the recommendations of Huang et al., (2012) and we excluded from the study individuals with a string of consistent responses equal or greater than 10 (i.e., half of the length of the total scale). Furthermore If a participant responded to less than 50% of the items on a scale, we excluded that participant's score for that scale. Finally we decided not to exclude outliers as we believe that this would have led to the loss of important information and we did not perform any transformation of the data.

Ethics Information, Administrative Organization and Data protection

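### The stopping Bayes factor ignores neuroticism, although it is scored before randomisation and no baseline stress score exists; this costs precision but causes no bias

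*Combined protocol and SAP*

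**What the plan says.** All references are to the combined protocol and SAP.

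- **Order of measurement** (Study 2, *Procedure*). "After the completion of the neuroticism measure, participants were randomly allocated to one of the five conditions". State STAI is first completed after the 15-minute recording, followed by the Self-Assessment Manikin and then demographics. No stress score before the recording is described.
- **Confirmatory test** (*Confirmatory analyses*). "we carried out four independent-samples Bayesian t-tests to determine whether there was a difference between each mindfulness exercise and the active control condition". The plan then adds: "To account for the hierarchical nature of the data, we compared the condition means using a Bayesian mixed-effects model that involved a random intercept", with lab and control story as the grouping factors. The sequential testing belongs to this phase: the Bayes factor is checked every 3 days and an arm's test stops at 10 or 1/10.
- **Neuroticism** (*Exploratory analyses*). It is used only to test moderation, where "we compared the model with the interaction to the model with only the main effects". The plan states that exploratory analyses do not affect sampling decisions.
- **Design analysis** (*Bayesian design analysis*). "The design analysis, however, assumed a conservative scenario with equal" N in all conditions, which reduces it to one two-group t-test without a covariate.
- **Completeness** (*Dealing with careless or insufficient effort responder*). "for the questionnaires related to our dependent variables/moderator instead the answers were requested" and not forced, so some neuroticism scores may be missing.

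**The concern.** With no baseline stress score, all stable differences between people in STAI go into the error term. Neuroticism is the one participant characteristic measured before allocation that the plan itself links to stress: it is studied as a moderator, and *Study 1, Procedure* describes traits that predispose people to more stress. Because it precedes randomisation, adjusting for it is legitimate.

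Leaving it out does not bias the comparison. What is at stake is how often the sequential test ends correctly. By the plan's own figures, with a true effect near d = .20, 7% of tests stop wrongly at H0 and 21% run to the maximum without reaching a boundary. A wrong stop closes that exercise's confirmatory test. A covariate that reduces residual variance lowers both percentages without recruiting anyone.

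**Working it through.** **Inputs from the plan.** Two-sided JZS Bayes factor with r = √2/2. Boundaries 10 and 1/10. True effect drawn from N(.20, .05) once per simulated trial. Minimum per condition 70 × 30 / 5 = 420 and maximum 120 × 30 / 5 = 720. The spacing of looks in the design analysis is not stated; every 10 per group is assumed.

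**Input not in the plan.** The correlation ρ between neuroticism and post-recording STAI. The range 0 to .6 is assumed.

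**Step 1: reproduce the plan.** First look at 420 per group, maximum 720, no lab or story effects, 40,000 simulated trials:

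| | Plan | Reproduced |
|---|---|---|
| H1 boundary | .72 | .720 |
| H0 boundary (wrong) | .07 | .066 |
| At maximum: BF > 3 / inconclusive / BF < 1/3 | .05 / .13 / .03 | .052 / .131 / .031 |
| Mean N per condition | 526 | 525 |

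**Step 2: add neuroticism.** Adjustment cuts the residual variance to (1 − ρ²), so the standardised effect is multiplied by 1/√(1 − ρ²). The adjusted n with the precision of 720 unadjusted is 720(1 − ρ²).

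| ρ | Multiplier | P(H1) | P(wrong H0) | Mean N | Equivalent of 720 |
|---|---|---|---|---|---|
| 0 | 1.000 | .720 | .066 | 525 | 720 |
| .1 | 1.005 | .725 | .064 | 523 | 713 |
| .2 | 1.021 | .738 | .061 | 520 | 691 |
| .3 | 1.048 | .760 | .054 | 515 | 655 |
| .4 | 1.091 | .788 | .047 | 506 | 605 |
| .5 | 1.155 | .825 | .037 | 494 | 540 |
| .6 | 1.250 | .870 | .026 | 479 | 461 |

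A separate run with 200,000 trials per cell agrees to within .01.

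**Step 3: no true effect.** H0 stops are about .85 and false H1 stops .005 to .006 at every ρ. In this calculation that follows by construction, since the multiplier acts on zero.

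**Step 4: first look at 100 per group.** *Confirmatory analyses* starts monitoring there. P(H1) and P(wrong H0) are .728 and .099 unadjusted, .745 and .092 at ρ = .2, .793 and .073 at .4, and .872 and .043 at .6.

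**Step 5: bias.** In 6,000 simulated trials (420 per group, d = .20, ρ = .5) the mean estimate was .200 unadjusted and .201 adjusted. The empirical SE was .068 and .060; theory gives √(2/420) = .069, and .069 × √.75 = .060.

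**Step 6: lab effects and missing scores.** Participant-level simulation with 30 labs of 24 per arm, an assumed lab ICC of .05, lab as a fixed effect, and looks every 30 per group from 420 to 720 (6,000 trials per cell). P(H1) rises from .70 to .72 at ρ = .2, from .70 to .77 at .4, and from .71 to .86 at .6. With 5% of neuroticism scores missing and replaced by the mean, the gains are .01, .07 and .14.

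**Step 7: story variance.** Neuroticism cannot remove it. With between-story SD τ (in STAI SDs) over three stories, the gain in effective sample is

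(2/n + τ²/3) / ((1 − ρ²)·2/n + τ²/3) − 1.

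For n = 720 and ρ = .4, 2/n = .002778:

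- τ = 0: 1/.84 − 1 = 19%
- τ = .05: .003611/.003167 − 1 = 14%
- τ = .10: .006111/.005667 − 1 = 8%

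**Step 8: restricted range.** *Participants and sites* says: "Participants were excluded if they reported having or having had a history of mental illnesses". If that cut the neuroticism SD by 20% (u = .8, assumed), ρ = .4 would become ρu/√(1 − ρ² + ρ²u²) = .32/√.9424 = .33.

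**The case against.** **This is efficiency, not error.** The design analysis and the confirmatory test are both unadjusted, so the plan is consistent, and it judges its own informativeness adequate. This stands: the point is an improvement, not a correction.

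**The deciding number is missing.** Nothing in the documents favours ρ = .4 over .2, and the mental-illness exclusion points downward. This also stands. It limits the claim to a range, and at .2 or below the gain is 2 points or less.

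**The headline gains are not for the planned model.** Adding τ²/3 to the contrast variance (τ treated as known) gives P(H1) of .615 unadjusted, .626 at ρ = .2 and .678 at .4 for τ = .05. For τ = .10 it gives .388, .396 and .423. At ρ = .4 the gain is then about 6 or 3.5 points instead of 7. Re-allocation also matters. If two exercises stopped near 500, the other three groups could reach (3600 − 1000)/3 ≈ 867. With a maximum of 870, P(H1) is .79 unadjusted, .80 at ρ = .2 and .845 at .4, a gain of about 5.5 points at .4. These reductions are real, but the gain stays positive in every case.

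**The fix has costs.** The stopping statistic would now depend on a scale with unforced answers, need an imputation rule, and change the meaning of the prior scale. All three can be settled in advance.

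**An adjusted estimate is already available.** The main-effects model in *Exploratory analyses* contains condition and neuroticism. That is only a partial answer, because the model does not drive stopping.

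**Conclusion.** The point holds. The confirmatory and monitoring Bayes factor omits a prognostic candidate that the plan already collects before randomisation. There is no bias, and essentially no change when there is no true effect. With d near .20 and the plan's 420-to-720 design, adjustment raises the chance of reaching H1 by about 2 points at ρ = .2, 7 at .4 and 15 at .6. Wrong H0 stops fall from .066 to .061, .047 and .026. Story variance or larger groups after re-allocation would make the gain in reaching H1 smaller.

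Confidence in the size is moderate. The correlation, the lab ICC and the story SD are all assumed, and the full Bayesian mixed model was not simulated. The change is recommended because it costs little if ρ is low and pays off from about .4.

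**What to change.** - Prespecify centred neuroticism as a fixed main effect in both models, with and without condition, that form the confirmatory and 3-day monitoring Bayes factor. Fix its prior before monitoring starts.
- Leave the lab and story random intercepts as they are for this purpose, and keep the neuroticism-by-condition interaction exploratory.
- State a missing-score rule. The plan drops a scale score "If a participant responded to less than 50% of the items on a scale". When that happens to neuroticism, impute the overall mean across all arms so that no participant is lost.
- Report the Bayes factor without neuroticism as a sensitivity result.
- State that the Cauchy r-scale now refers to the residual SD, and report the effect on the raw SD scale as well.
- Restate the design analysis for the adjusted test over a range of assumed correlations that includes .2 or lower.

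The cost is one extra term in two models, the missing-score and prior statements, and a rerun of the design simulation. No new data are needed.

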We implemented the sequential design as being adaptive, stopping collecting the data for a given test of a condition after obtaining a Bayes Factor of 10 in favor of H_1 or a Bayes factor of 1/10 in favor of $H_{0.}$, and re-assigning the remaining participants into other conditions, where such a threshold has not been met. We chose a Bayes Factor of 10, because according to the classification of Lee and Wagenmakers (2013), it demarcates the threshold between moderate and strong evidence. We started monitoring the Bayes Factor when there were at least 100 participants in each group. We chose 100 arbitrarily, because with a smaller sample size, the probability of misleading evidence (i.e., a Bayes Factor trajectory that arrives at the "wrong" boundary, that is, at the H_0 boundary when H_1 is correct and the other way around) would have been higher. Here, using a sample size of 100 and a Bayes Factor of 10 we aimed to substantially decrease the probability of misleading evidence (Stefan et al., 2017).

We monitored the Bayes Factor and recorded the interim analysis every 3 days to check whether the threshold was reached⁷. If the threshold was not reached (BF of 10 or of 1/10) we stopped the data collection after that the maximum number of participants⁸ was reached. If for any of the four tests, one of these three conditions was not met (i.e., BF of 10 in favor of H₁; BF of 1/10 in favor of H₀; the maximum number of participants is reached), the data collection was terminated four months after the start of the experiment. When one of these three conditions has been met, we stopped allocating participants to that particular experimental condition and we allocated them to the remaining conditions for which this has not been the case yet. If the data collection ends before all the sites are able to collect at least 70 participants⁹ (because we would have reached a Bayes Factor of 10 in favor of H₁ or of 1/10 in favor of H₀ for a given test of a condition), we will continue with the data collection by reopening all groups and equitably allocating each participant to each group until each site would have collected at least 70 participants. In this case, we would use this sample for exploratory analyses.

Exploratory analyses

We also carried out analyses exploring the effect of experimental conditions on pleasure, arousal, and dominance, and for the potential moderating effect of neuroticism. We

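### The monitoring start at 100 per group is credited with reducing misleading evidence at both boundaries, but it can act only on false H1 evidence and leaves wrong H0 closure unchanged

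*Combined protocol and SAP*

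**What the plan says.** All of this is in Analysis Plan, Confirmatory analyses, unless noted.

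- **Rule.** Each exercise is compared with the control until "obtaining a Bayes Factor of 10 in favor of H_1 or a Bayes factor of 1/10 in favor of" H0, with Bayes factors checked every 3 days. An exercise that reaches a boundary receives no further participants.
- **First look.** "We started monitoring the Bayes Factor when there were at least 100 participants in each group".
- **Reason.** "We chose 100 arbitrarily, because with a smaller sample size, the probability of misleading evidence" would be greater. A misleading trajectory is defined as one that arrives "at the H_0 boundary when H_1 is correct and the other way around", so both errors are meant. The text adds that "using a sample size of 100 and a Bayes Factor of 10 we aimed to substantially decrease the probability of misleading evidence".
- **Prior and model.** "We employed a two-tailed test using a non-informative JZS Cauchy prior for the alternative hypothesis with a default" scale of √2/2. Condition means are then compared with "a Bayesian mixed-effects model that involved a random intercept for lab and for different stories".
- **Design analysis** (Bayesian design analysis section). It uses a single equal-n t-test with effects drawn from N(0.20, 0.05), a minimum of 420 and a maximum of 720 per condition. It reports .72 at H1, .07 wrongly at H0, .21 at the maximum, and an average n of 526.

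**The concern.** Evidence for H0 from a JZS Bayes factor builds slowly, because the wide prior on the effect has to be ruled out. At small n the H0 boundary may be out of reach whatever the data show. If so, a minimum sample size below that point cannot reduce wrong H0 closures, and the stated reason fails for the first of the two errors it names.

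That error is the larger one in this design. An effective exercise that reaches the H0 boundary loses its remaining allocation and is reported as having strong evidence against an effect. A team that believes the start at 100 guards against this will not look for something that does.

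**Working it through.** **Inputs.** Two-sided JZS prior with r = √2/2; boundaries BF10 = 10 and 1/10; first look 100 per group; effects N(0.20, 0.05); minimum 420 and maximum 720 per condition. Participants per look are not stated. I assume looks every 10 per group, and show 1 and 50 as a range.

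**Formula.** With N = n₁n₂/(n₁+n₂) and ν = n₁+n₂−2,

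BF10 = ∫ (1+Nr²g)^(−1/2) · [1 + t²/((1+Nr²g)ν)]^(−(ν+1)/2) · p(g) dg ÷ (1+t²/ν)^(−(ν+1)/2), where p(g) = (2π)^(−1/2) g^(−3/2) e^(−1/(2g)).

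**Step 1: reproduce the plan's figures.** Simulated equal-n trajectories to 720, looks every 10:

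| First look | H1 | Wrong H0 | Maximum n | Average n |
|---|---|---|---|---|
| Plan states | .72 | .07 | .21 | 526 |
| 420 | .719 | .068 | .212 | 525 |
| 100 | .728 | .098 | .173 | 397 |

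The published set matches a first look at 420, not at 100.

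**Step 2: earliest possible H0 closure.** The data most favourable to H0 are t = 0. There ν drops out and BF01 depends only on N.

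| n per group (equal) | 100 | 200 | 246 | 247 | 420 |
|---|---|---|---|---|---|
| Largest possible BF01 | 6.50 | 9.03 | 9.98 | 10.003 | 12.96 |

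So N must reach about 247/2 = 123.5. With unequal groups the exercise arm can be smaller: 210 × 300/510 = 123.5, so 210 is enough with 300 controls. Because N is always below n₁, the exercise arm needs about 124 however large the control group is. With 100 in the exercise arm, BF01 cannot exceed 9.03.

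**Step 3: what the start changes** (looks every 10).

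| First look | Wrong H0, effects N(.20, .05) | Wrong H0, d = 0.20 | False H1, true null |
|---|---|---|---|
| 20 | .097 | .054 | .029 |
| 50 | .098 | .054 | .023 |
| 100 | .098 | .054 | .017 |
| 200 | .098 | .054 | .011 |

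A separate simulation with looks every 9 per group gave false H1 of .026 and .015 for starts at 20 and 100. With the start at 100 and effects N(.20, .05), wrong H0 is .108, .098 and .081 for looks every 1, 10 and 50 per group.

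**Step 4: a later floor for H0 only** (H1 from 100, H0 from 420, looks every 10, 40,000 trials).

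| Truth | Quantity | Single floor 100 | H0 floor 420 |
|---|---|---|---|
| N(.20, .05) | Wrong H0 | .099 | .067 |
| | H1 reached | .727 | .733 |
| | Average n per group | 396 | 416 |
| d = 0.20 | Wrong H0 | .054 | .027 |
| Null | Correct H0 | .875 | .848 |
| | Average n per group | 387 | 489 |

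**Step 5: scaling with sites.** Five conditions share the participants. The 70-per-site minimum gives 70k/5 = 14k per group, and the 120k cap (footnote 8) gives 24k. At k = 30 these are 420 and 720. At k = 17, 14k = 238, below 247, so the floor no longer binds. A fixed 420 at k = 17 would exceed the equal-allocation cap of 24 × 17 = 408.

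**The case against.** The strongest reply has four parts.

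1. **The plan credits 100 jointly with BF 10, calls 100 arbitrary, and says in the Analysis Plan that error-rate control is not the aim.** This stands in part. The threshold does limit wrong H0 closure, and the start does reduce false H1 evidence. A reader might infer that the design has no protection against wrong H0 closure; the documents do not support that. But the sentence on 100 says that a smaller sample would raise misleading evidence, and for the H0 side that is untrue. Disclaiming error control does not rescue a reason that is itself stated as an error probability.

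2. **The planned model has random intercepts for lab and story, and the calculation does not.** This stands. A reader might take 247 as a hard bound for the actual analysis, but the exact bound there cannot be derived from the documents. The plain t-test is used because the plan's own design analysis uses it.

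3. **The rate near .10 averages over weaker effects.** This stands. At the effect the study intends to detect, d = 0.20, it is about .05. Both belong in the report.

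4. **A floor fixed at 420 presumes 30 sites, while the plan expects up to 30.** This stands, and is why the floor should be written in terms of k.

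**Conclusion.** The rationale for the start at 100 is half right. The start lowers false H1 evidence and has no effect on wrong H0 closure; any limit on the latter comes from the Bayes factor threshold. The 247 figure assumes the stated prior, a plain t-test and equal groups; about 124 in the exercise arm is the lower limit at any control-group size. The simulated rates also depend on look spacing, which the documents do not give in participants.

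The monitoring rule can be run as written, and a reader should not infer that its Bayes factors are invalid. The practical consequence is that the reported .07 describes a later start than the plan specifies. Monitoring from 100 gives about .08 to .11 with effects N(.20, .05). The change is advisable rather than essential.

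**What to change.** **Rationale.** State that the start at 100 acts on false H1 evidence only. Add that, in the t-test simplification with equal groups, the H0 boundary is unreachable below about 247 per group.

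**Rule.** Keep 100 per group for closure in favour of H1. Allow no closure in favour of H0 before 14k per group, where k is the number of participating sites (420 at k = 30). With about 17 or fewer sites this floor has no effect.

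**Cost at 30 sites.** One sentence and one condition in the monitoring code. If an exercise is truly null, correct H0 closures fall from about .88 to .85 and average n rises by about 100 per group (489 − 387 = 102). With all four exercises null and reallocation, the average total rises from about 2,430 to 2,860 (430/2,430 ≈ 18%), still below the cap of 3,600.

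**Alternative.** If the sponsor prefers a single floor of 100, the Bayesian design analysis section should give a wrong-H0 probability of about .08 to .11 with the look spacing stated, and an average n of about 376 to 436 per condition in place of 526.
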